Participants (N = 130) will be randomly assigned to a Usual Care Control or IPS Plus Abstinence-Contingent Wage Supplements group. Computerized urn randomization (Wei & Lachin, 1988) will balance groups on characteristics that may influence outcome: (1) percent of days abstinent from alcohol (assessed by transdermal alcohol concentrations prior to random assignment; \geq rolling median, Y/N); (2) evidence of opiate and cocaine use from the assessment prior to random assignment (Y/N); (3) completed high school or obtained a GED (Y/N); and (4) gender (male/female). Participants will be stratified by alcohol and drug use because they should predict alcohol abstinence during the intervention period. High school completion or GED should be associated with employment. Participants will be stratified by gender to balance the two groups on a key biological factor that may influence outcome.

Individual Placement and Support (IPS) & Abstinence-Contingent Wage Supplement Group

This group will receive the full intervention being evaluated in this study for 6 months.

Individual Placement and Support (IPS). After Phase 1, participants will be offered the IPS model of supported employment for 6 months. IPS involves rapid job search, promotes competitive employment, and provides job supports and benefits counseling.

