Verification of employment. To gain verified and objective records of employment, we may get an objective measure of each participant's employment history by getting each participant's earnings history using federal Form SSA-7050-F4 (10-2016) UF, REQUEST FOR SOCIAL SECURITY EARNINGS INFORMATION. Participants and research staff will complete this form and have the participant's earnings history sent to our research unit. Our research unit will pay for the costs of this service. We may request these documents one or more times. We will take the following steps to protect this sensitive information in our study databases: (1) when storing a completed form, we will redact name, date of birth, and social security number from the written document and label the document with an ID number; (2) keep paper copies in a locked file cabinet in a locked office and never keep documents out while unattended by research staff; and (3) only enter relevant information into the database (i.e., information about when participants worked, how much they earned, and what type of employment they had). The risks associated with collecting this information are explained on the consent form.

b. Study duration and number of study visits required of research participants.

Participants will be invited to enroll in Phase 1 of the therapeutic workplace for 1 month. All participants that report to be assessed at the end of Phase 1 and are willing to continue to wear a wearable alcohol biosensor will be randomly assigned to the study groups and followed for 6 months. All participants will be invited to participate in an intake assessment to determine eligibility and characterize the population. Outcome assessments will be conducted immediately prior to random assignment, every 30 days throughout the 6-month intervention evaluation period after random assignment and then at 6 and 12 months after the end of the intervention evaluation period. These assessments may be collected using REDCap and conducted via phone or web-conferencing.

NA

c. Blinding, including justification for blinding or not blinding the trial, if applicable.

NA

d. Justification of why participants will not receive routine care or will have current therapy stopped.

NA

e. Justification for inclusion of a placebo or non-treatment group.

NA

f. Definition of treatment failure or participant removal criteria.

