Self-Reported Alcohol Use (secondary aim). Assess the effectiveness of *IPS Plus Abstinence-Contingent Wage Supplements* in reducing self-reported alcohol use during the intervention. We will use three self-report measures of alcohol use (based on TLFB) during the 30 days prior to each of the 6 monthly assessments during the year after random assignment. We will assess: 1) the percent of days abstinent from alcohol; 2) the average number of standard drinks per drinking day ingested; and 3) the percent of heavy drinking days (≥ 5 standard drinks per day for men and ≥ 4 standard drinks per day for women). Hypothesis: We expect that *IPS Plus Abstinence-Contingent Wage Supplement* participants will have less self-reported alcohol use during the intervention after random assignment relative to Usual Care Control.

Employment (secondary aim). Assess the effectiveness of *IPS Plus Abstinence-Contingent Wage Supplements* in promoting employment during the intervention. We will assess the number of days participants are employed during the 30 days prior to each of the 6 monthly assessments during the intervention after random assignment. Hypothesis: We expect that *IPS Plus Abstinence-Contingent Wage Supplements* will increase employment during the intervention after random assignment relative to Usual Care Control.

Post-Intervention Effects (secondary aim). Assess the effectiveness of IPS Plus Abstinence-Contingent Wage Supplements in promoting employment and abstinence from alcohol after the intervention ends. We will compare the groups on self-reported measures of alcohol use and employment at 6- and 12-month follow-up assessment time points after the intervention ends. Hypothesis: We expect that IPS Plus Abstinence-Contingent Wage Supplements may need to be maintained to promote long-term employment and abstinence from alcohol, and thus alcohol abstinence and employment may not be sustained after the intervention ends.

Economic Outcome Measures

Costs of Treatment (secondary aim). Assess the costs of treatment for Usual Care and IPS Plus Abstinence-Contingent Wage Supplements. We will assess the total cost per participant in both study groups. Hypothesis: We expect that treatment costs for IPS Plus Abstinence-Contingent Wage Supplements will be higher per person relative to Usual Care due to the IPS and wage supplements and because we expect that IPS Plus Abstinence-Wage Supplement participants will have greater treatment engagement.

[figure not shown]

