regression and GEE will be expressed using odds ratios with 95% CI. Analyses will include all randomized participants as intent-to-treat, and will be adjusted for pre-specified covariates used for stratification (Pocock et al., 2002). Tests will be two-sided and, because we have one primary outcome, alpha will be set at 0.05. Based on our previous experience, we expect rates of attrition at monthly visits to be low. If rates are higher than expected, we will use mixed effects models rather than GEE estimation, as the former has less strict assumptions regarding missing data (MAR, rather than MCAR). If it appears that the missing data are MNAR, then we will fit pattern mixture models as described by Hedeker & Gibbons (1997).

Missing data. We expect to collect >90% of assessments. Our approach to handle missing data will be to impute all missing values as the adverse outcome (e.g., alcohol positive). Model parameter estimates from this approach will be compared to a method without imputation. If these methods yield differing results, conclusions will need to be tentative, but results from both approaches will be reported in publications. To investigate sensitivity to missing values, participants with and without missing values will be compared by covariates and treatment assignment. If rates of missingness are higher than expected, we may use multiple imputation (Rubin, 1996) or pattern mixture models (Hedeker & Gibbons, 1997) to obtain unbiased estimates of treatment effects.

Consideration Of Sex And Other Variables In Moderating The Outcomes

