We will conduct analyses to identify biological and other variables that moderate the outcomes of employment and alcohol abstinence. We will examine efficacy differences as a function of four variables assessed prior to random assignment by including interaction terms in our regression models: 1) Percent of days abstinent from alcohol (based on transdermal alcohol concentrations) prior to random assignment. 2) Opiate- and cocaine-negative urine samples from the assessment prior to random assignment. 3) Completed high school or obtained a GED; and 4) gender (male/female). Alcohol use and opiate/cocaine use prior to random assignment should be associated with higher rates of alcohol use and lower rates of employment during the 6 months after random assignment. We expect that high school completion or obtaining a GED will be associated with higher rates of employment. Gender is a key biological factor that may influence outcome. We also expect that the effect of IPS Plus Abstinence-Contingent Wage Supplements will be affected by these variables.

Balancing of potential moderators of treatment response via urn randomization merely ensures that the estimation of the treatment effect is unbiased. Balancing the randomization by these variables allows for them to be adjusted for in subsequent analyses. It does not take the place of these adjustments. Moderator analysis entails fitting a model with the main effects of treatment and the putative moderating variable, and their interaction. Likewise, balancing the variables during randomization does not take the place of fitting this interaction. For more discussion, see Pocock et al. (2002).

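### The self-reported drinking models leave out each measure's own pre-randomization value, which gives up some power on secondary outcomes

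*Combined protocol and SAP*

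**What the plan says.** Section 7.c (Main analysis) applies a longitudinal binomial regression with GEE to all repeated measures and reports odds ratios. Its only statement on covariates is that analyses "will be adjusted for pre-specified covariates used for stratification".

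Section 4.a (Experimental Design) lists four urn factors. The alcohol factor is "percent of days abstinent from alcohol (assessed by transdermal alcohol concentrations prior to random assignment", split at the rolling median. The others are "evidence of opiate and cocaine use from the assessment prior to random assignment (Y/N"), high school or GED completion, and gender.

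Section 7.b defines the self-report outcomes: "We will use three self-report measures of alcohol use (based on TLFB) during the 30 days prior to each of the 6 monthly assessments". They are percent days abstinent, drinks per drinking day and percent heavy drinking days. For the period after the intervention it adds: "We will compare the groups on self-reported measures of alcohol use and employment at 6- and 12-month follow-up assessment time points".

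Section 4.b sets the schedule: "Outcome assessments will be conducted immediately prior to random assignment, every 30 days throughout the 6-month intervention evaluation period".

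The moderator part of Section 7.c states the premise that earlier drinking is prognostic: "Alcohol use and opiate/cocaine use prior to random assignment should be associated with higher rates of alcohol use" during the six months after randomization.

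**The concern.** The plan adjusts for baseline factors because it expects them to predict outcome. For a self-reported drinking outcome, a natural predictor is the same measure, from the same instrument, taken before randomization. It appears in none of the models.

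The biosensor factor replaces it only in part. It is a yes/no split and counts days rather than amount, whereas two of the three self-report measures concern heavy or intense drinking. The sensor is issued only after the one-week induction, so the factor covers about three weeks. It is also a different instrument.

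What is at stake is the precision of the self-report comparisons, during the intervention and at the two later follow-ups. At those follow-ups self-report is the only alcohol comparison planned, and it rests on at most 130 people.

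**Working it through.** **1. The plan's own figure.** Section 7.c gives 130 × 0.90 = 117, which reproduces. It says 117 is slightly above the largest N required for a 15-point difference at 80% power. For repeated binary data, total N = 2n × [1 + (m − 1)ρ]/m. The worst case is 42.5% against 57.5%, with n = 174 per group (two-sided 0.05) and m = 6:

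- ρ = 0.20: 348 × 2.0/6 = 116
- ρ = 0.30: 348 × 2.5/6 = 145
- ρ = 0.50: 348 × 3.5/6 = 203

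The statement therefore fits ρ near 0.20. The readable text gives no ρ, because the figure is not shown. This calculation concerns the primary outcome; the plan states no power for the self-report outcomes.

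**2. Is the baseline used anywhere else?** No. The moderator models reuse the four urn characteristics. The follow-up moderator models use values from the intervention period. Section 7.b defines the outcomes on post-randomization assessments, so the baseline is not a modelled response either.

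**3. Size of the loss, linear approximation.** All correlations are assumptions:

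- r, baseline TLFB with each follow-up value: 0.1 to 0.4
- ρ, between follow-up values: 0.2 and 0.5
- k, TLFB with sensor at baseline: 0.5 and 0.8
- the sensor measure, before splitting, is as prognostic as TLFB

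A median split keeps √(2/π) = 0.798 of a correlation, so s = 0.798r (stratum with outcome) and b = 0.798k (stratum with TLFB).

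- Variance of the mean of m assessments: V = [1 + (m − 1)ρ]/m
- Planned model: V − s²
- Further reduction from the own baseline: (r − bs)²/(1 − b²)

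Example with r = 0.3, ρ = 0.2, k = 0.5, m = 6: V = 0.333, s = 0.239, V − s² = 0.276, b = 0.399. The further reduction is (0.3 − 0.0955)²/(1 − 0.159) = 0.0497, and 0.0497/0.276 = 18.0%. With ρ = 0.5 and k = 0.8 it is 0.0366/0.526 = 7.0%.

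| r | Six monthly assessments | Two follow-ups |
|---|---|---|
| 0.1 | 0.7% to 1.7% | 0.5% to 0.9% |
| 0.2 | 2.9% to 7.2% | 2.2% to 3.8% |
| 0.3 | 7.0% to 18.0% | 5.3% to 9.2% |
| 0.4 | 13.5% to 38.2% | 10.0% to 17.8% |

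The upper ends need ρ = 0.2. At r = 0.3 or 0.4 the baseline would then correlate more strongly with each follow-up than the follow-ups do with one another. With ρ = 0.5, the monthly range is 7.0% to 9.5% at r = 0.3 and 13.5% to 18.4% at r = 0.4.

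**4. In participants and power at r = 0.3.** Equivalent N = 117/(1 − reduction): 126 to 143 for the monthly assessments, 124 to 129 for the follow-ups. A comparison with 80% power under the planned model would have Φ(2.802/√(1 − reduction) − 1.960), which is about 83% to 87% and 82% to 84%.

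**5. Check on the planned type of model.** Binomial GEE was simulated with 117 participants, 30-day windows and 250 runs per setting, with and without the baseline next to the sensor stratum. In one six-assessment setting with r about 0.30, the log odds ratio moved from 0.629 (SE 0.155) to 0.648 (SE 0.147), so z² rose by (0.648/0.147)²/(0.629/0.155)² = 1.18. Across settings, z² rose by about 8% to 18% (six assessments) and 4% to 12% (two follow-ups) at r about 0.30. At r about 0.48 it rose by 40% to 83% and 23% to 53%. Every setting favoured adjustment.

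**The case against.** The strongest reply is that the plan already does something valid. Adjusting for the stratification factors is prespecified and unbiased. Every model already carries a pre-randomization alcohol measure, and the urn limits chance imbalance on it. Percent heavy drinking days cannot exceed percent drinking days, so the sensor factor says something about heavy drinking too. This stands, and it is why the working counts only the gain beyond that stratum.

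The baseline month may also be a weak predictor. It falls in Phase 1, which is meant to initiate abstinence and may follow inpatient detoxification, and the follow-ups come 12 and 18 months after randomization. This also stands. At r near 0.1 the gain is negligible, and it is smaller at the follow-ups than in the monthly series throughout the table.

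Two stronger readings are tempting and are not supported.

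- A reader might infer that every participant certainly has a baseline value for all three measures. Section 4.b names no instruments for the pre-randomization visit, so TLFB there is a reasonable inference only. Anyone who did not drink in that window has no value for drinks per drinking day.
- A reader might multiply the standard error by √(1 − r²) and claim the equivalent of 33% more participants at a partial correlation of 0.5 (1/0.75), or 56% more at 0.6 (1/0.64). That is a linear-model result. With logistic GEE the conditional odds ratio moves as well as its standard error, as step 5 shows, so the gain has to be stated as power. Nor do the documents support correlations that high.

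**Conclusion.** The omission is real, and nothing else in the plan fills it. The direction of the loss follows from the plan's own premise that earlier drinking predicts later drinking. The size cannot be fixed from the documents. It is roughly 1% to 38% of variance for the six monthly assessments and 0.5% to 18% for the two follow-ups, for assumed correlations of 0.1 to 0.4, and 7% to 18% and 5% to 9% at 0.3. These figures rest on the correlations assumed in step 3, and on TLFB being part of the pre-randomization assessment.

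A reader might infer that the trial's main result or sample size is in doubt. It is not: this is a matter of efficiency for secondary outcomes, without bias, and the primary biosensor analysis and the N of 130 are unaffected. The percentages apply to the two outcomes that are proportions of days. Drinks per drinking day is not a proportion, so the stated binomial model does not fit it, and there is as yet no usable model to which its baseline could be added.

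**What to change.** In Section 7.c (Main analysis), state that the models for percent days abstinent and percent heavy drinking days, during the intervention and at the 6- and 12-month follow-ups, also include that measure's pre-randomization TLFB value as a continuous covariate, next to the four urn factors.

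For drinks per drinking day, first specify a suitable non-binomial model. Then include the baseline value together with an indicator for no baseline drinking days.

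In Section 4.b, confirm that TLFB is part of the assessment before randomization. Leave the primary biosensor model as it is.

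The cost is a few sentences, settled before outcome data are compared by group. If TLFB is given at that visit, no new data are needed. Few baselines should be missing, because Section 4.b makes attendance at the end-of-Phase-1 assessment a condition of randomization. The reported odds ratios become conditional on one more covariate, and the text should say so.

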We will conduct similar analyses to identify variables that moderate outcomes on employment and alcohol use during the follow-up year after the interventions have ended. We will examine differences in outcomes during the follow-up year as a function of three variables assessed at the end of the intervention period by including interaction terms in our regression models: 1) Percent days abstinent from alcohol from the last 3 months under the study interventions; 2) percent of opiate- and cocaine-negative urine samples from the last 3 monthly assessments under the study interventions; 3) Highest hourly wage that each participant earned during the year after random assignment. We expect that alcohol and opiate/cocaine use during the last 3 months under the study interventions will be associated with higher rates of alcohol use and lower rates of employment during the follow-up year. We expect that the highest wage achieved under the study interventions will be associated with higher rates of employment and lower rates of alcohol use during the follow-up year.

Economic Analyses

Our economic evaluation will be done from the provider perspective.

Cost Analysis. We will derive cost estimates of intervention activities following an activity-based approach (Drummond et al., 2005; Gold et al., 1996; [name], [name] et al., 2004; [name] et al., 2005; [name], [name], et al., 2008). The total cost per participant of each intervention will be the sum of the cost for (1) staff labor, (2) building space, (3) wage supplements, and (4) supplies or materials. The total intervention cost for each participant is the cost per activity multiplied by the number of activities or services received by the participant. Taking the mean across participants in an intervention yields the mean per participant cost of that intervention. Treatment attendance will be captured in the modified Economic Form 90 AIR/ED. Standard addiction treatment costs will be drawn from the literature (e.g., [name] et al., 2004).

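### The wage predictor for the follow-up year is defined over a window that runs into the follow-up year, and the three follow-up moderators are post-randomization variables that need a caveat on interpretation

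*Combined protocol and SAP*

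**What the plan says.** The moderator subsection of Section 7c plans two sets of analyses.

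- **Intervention period.** "We will examine efficacy differences as a function of four variables assessed prior to random assignment". The model is spelled out: "Moderator analysis entails fitting a model with the main effects of treatment and the putative moderating variable, and their interaction".
- **Follow-up year.** The plan calls these analyses similar to the first set. The aim is put this way: "We will examine differences in outcomes during the follow-up year". The differences are to be studied "as a function of three variables assessed at the end of the intervention period by including interaction terms in our regression models". The variables are "Percent days abstinent from alcohol from the last 3 months under the study interventions"; the percentage of opiate- and cocaine-negative urine samples at the last three monthly assessments; and "Highest hourly wage that each participant earned during the year after random assignment".

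The expectations stated for the second set are prognostic. Alcohol and drug use late in the intervention "will be associated with higher rates of alcohol use and lower rates of employment during the follow-up year", and "the highest wage achieved under the study interventions" is expected to go with more employment and less alcohol use.

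The Abstract (Section 1) and Sections 4a and 4b give a 6-month intervention. Section 4b places the follow-up assessments 6 and 12 months after it ends. Section 7b (Post-Intervention Effects) separately compares the randomized groups at those two assessments.

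**The concern.** **Wage window.** One paragraph gives the same variable two different periods: twelve months from randomization, and the period under the interventions, which is six months. Two analysts could build different variables from it. Under the longer period, the predictor shares calendar time with the employment outcome it is meant to predict, so part of any wage-employment association would arise by construction. That weakens even a purely prognostic reading.

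**Post-randomization moderators.** The first set uses only variables fixed before randomization; the second uses none. Section 7a expects treatment to raise abstinence during the intervention, and Section 7b expects it to raise employment, on which wage depends. Participants from the two arms with equal late abstinence, or equal best wage, are then not comparable by virtue of randomization. The variables are called moderators, and Section 7c has no sentence on how the treatment and interaction terms should be read. A reader could take a conditional treatment term as evidence about efficacy.

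**Working it through.** **Timeline, in months from randomization**

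1. Intervention: 0 to 6 (Sections 1, 4a, 4b).
2. Follow-up assessments: 6 + 6 = 12 and 6 + 12 = 18. The 18-month horizon of the cost-benefit hypothesis in Section 7b agrees.
3. Follow-up year: 6 to 18.
4. Wage window, literal: 0 to 12. Overlap with the follow-up year: 12 − 6 = 6 months, or 6/12 = 50% of the window.
5. Wage window if limited to the intervention: 0 to 6. Overlap: 0 months.
6. The literal window closes at the month-12 assessment. Section 7b gives employment a 30-day look-back during the intervention. If follow-up employment uses the same look-back (an assumption), all 30 days at month 12 lie inside the literal window, against 0 of 30 if it ends at month 6. The look-back at month 18 lies outside under either reading.

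The variable is a maximum, so the choice changes its value only for participants whose highest wage came after month 6. For someone with no job until month 8, the literal variable exists only because that person worked in the follow-up year.

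**Direction of the conditional treatment term**

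The plan gives no figure to reproduce here. As a linear approximation,

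conditional difference ≈ true follow-up difference − (within-arm slope of outcome on moderator) × (treatment effect on moderator).

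The only input from the plan is the 15-point difference in the Power Analysis, used as the effect on late abstinence. The rest is assumed: late abstinence 35% or 50% in control, follow-up abstinence 40% in control, between-person logit SD 1.5, continuous moderator, true follow-up difference 0.

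| Assumed within-arm correlation | Simulated shift (points) | Conditional OR | Implied slope |
|---|---|---|---|
| none | 0 | 1.00 | 0 |
| 0.25 | about −7 | 0.73 | 7/15 = 0.47 |
| 0.36 | about −10 | 0.61–0.63 | 10/15 = 0.67 |
| 0.45 | about −12 | 0.51–0.53 | 12/15 = 0.80 |

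The size scales with the treatment effect on the moderator. With 5 points instead of 15, the formula gives 0.47 × 5 = 2.3 to 0.80 × 5 = 4.0 points; simulation gave 2.5 to 4. With no effect on the moderator there is no shift.

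A second simulation used N = 130, effects on the moderator of 0.65 or 1.2 log-odds, and an unmeasured common cause with coefficient 0.5, 1 or 1.5. It gave conditional ORs of 0.29 to 0.57, while the treatment-only model gave 1.00. The spread between the two simulations shows that the size is set by the assumptions. The sign was the same wherever treatment raised the moderator and moderator and outcome shared a cause.

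The interaction test rejected in 4–6% of runs at trial size in both simulations. In the second, a non-zero interaction coefficient (about 0.7) was clearly established only with N = 200,000.

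**The case against.** The strongest reply is that the plan never claims what the caveat guards against. For the intervention period it speaks of efficacy differences and expects the treatment effect to vary. For the follow-up year it speaks only of differences in outcomes and lists prognostic expectations, which are legitimate. It does not name treatment as the interacting variable; that follows from the word similar together with the model given for the first set, a fair inference but still an inference. The randomized follow-up comparison is planned separately. All of this stands, and it limits the remedy to a caveat and a relabelling.

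It also stands that the simulated shift concerns the treatment term, which the plan does not say it will interpret, whereas the text names interaction terms, for which no material distortion appears at this sample size.

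On wage, the mismatch is probably a drafting slip, and two phrases in the paragraph already point to the intervention period. That makes the correction easy, but the operative definition still says one year.

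A reader might infer three stronger things that the documents do not support:

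- **That the plan's follow-up efficacy conclusion is biased.** That conclusion comes from the randomized comparison in Section 7b.
- **That late abstinence is a piece of the primary outcome.** The follow-up-year list does not say that it is transdermal, as the baseline list does; it could be the self-reported measure. Nor does the plan predict a treatment effect on the opiate and cocaine results.
- **That half of the wage data are contaminated.** Half of the window overlaps, but a maximum changes only for some participants.

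**Conclusion.** Both parts hold, at minor severity.

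The wage definition contradicts its own paragraph and the 6-month intervention. As written, 6 of its 12 months lie in the follow-up year, and it runs up to one of the two follow-up assessments. This rests on the documents' dates alone. How many participants would have a different value is unknown, because it depends on who earned their best wage after month 6.

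The three variables are all post-randomization, and the plan expects treatment to change abstinence and the employment behind wage. Terms conditional on them are associations, not treatment effects in subgroups. If the treatment term were nevertheless read as an effect, it would be shifted against the intervention, provided that treatment raises the variable and that variable and outcome share causes. The simulations show that direction only; they do not estimate its size for this trial.

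The scope is one exploratory analysis. The primary analysis, the sample size and the randomized follow-up comparison are unaffected.

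**What to change.** 1. Define the wage variable as the highest hourly wage from randomization to the end of the 6-month intervention. Cost: a wording change. This removes the overlap but leaves the variable post-randomization, so item 2 is still needed.
2. State that late abstinence, urine results and wage are reported as exploratory prognostic associations, that the treatment and interaction terms in these models are not subgroup treatment effects, and that treatment conclusions for follow-up come from the randomized comparison in Section 7b. Cost: a sentence or two. Whether end-of-intervention status relates differently to later outcomes in the two arms can still be described.
3. If effect modification in the follow-up year is wanted, use the four pre-randomization variables already listed in Section 7c, labelled exploratory. No new data are needed, but this adds a few interaction tests, so it is more than a wording change.
4. Optional: Section 7b places the six monthly self-report assessments within a year of randomization, but the matching employment outcome within the intervention. Aligning the two is a tidy-up that changes no result, since the six assessments already fix the period.
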